10. EMERGENCY PROCEDURES

10.1 *Emergency Sponsor Contact*

In emergency situations, the subject should phone the number listed on the subject information sheet.

10.2 *Emergency Treatment*

During and following a subject's participation in the trial, the investigator/institution should ensure that adequate medical care is provided to a subject for any adverse events, including clinically significant laboratory values, related to the trial. The investigator/institution should inform the subject when medical care is needed for intercurrent illness(es) of which the investigator becomes aware. Any participant with potential cardiac emergency will be directed to the nearest hospital Emergency Room.

11. STATISTICAL PROCEDURES

11.1 *Analysis Variables*

Analysis of efficacy will be performed according to intention-to-treat method and include all subjects who received the combination antibiotic therapy. However as the primary efficacy analysis is of subjects with paired FFR assessments, only such subjects will be included in the primary analysis. All other subjects will be included in secondary analyses. Numerical data will be presented as mean \pm SD for normally distributed variables and as median with interquartile range for non-normally distributed data. Non-normally distributed data will be log-transformed (e.g. CRP levels) before being used for comparisons. Significant changes in subjects' arterial flow, clinical symptoms and biochemical variables over time compared with that baseline will be assessed using an analysis of covariance. Differences between treatment and control groups in the occurrence of FFR \geq 80 will be assessed using Fisher's exact test. All tests will be 2-tailed with a 5% significance level.

11.2 *Interim Analysis*

A DSMB directed interim analysis is planned when 60 paired FFR data are available. At this time point, the trial would declare the combination therapy as effective if the p value is less than 0.05. However, the trial might still continue to collect extra data to accurately characterise side effects as advised by the DSMB.

11.3 *Sample Size Justification*

This is a feasibility study designed to provide preliminary observations and generate hypothesis for future studies. The sample size of 60 subjects with paired FFR was not defined on the basis of a clinical endpoint hypothesis but rather to provide information about antibiotic combination therapy efficacy and safety. The sample size required is established by assessment of the minimum number of subjects needed to provide reliable and non-trivial results. The sample size is in the range of the intervention group in the azithromycin clinical trial of subjects with CAD (n=60).

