Efficacy Data	FBC, ESR, Electrolytes/Urea/Creatine, Liver Function tests, Lipid Studies ,CK-MB, High Sensitivity Troponin T, Chlamydophila pneumoniae titer, Chlamydophila pneumoniae macrophage culture, Chlamydophila pneumoniae (c. pneumoniae) DNA detection (exploratory), hs CRP, symptomatology, Functional Status – New York Heart Association Class, Quantitative Coronary Angiography (QCA); FFR and Coronary pressure/flow indices, plaque volume, plaque composition, fibrous cap thickness, macrophage content.
Safety data	Adverse event reports, Blood tests (standard haematology, serum chemistry and pregnancy) and Physical Examination, compliance and major adverse cardiac events MACE
Statistical procedures	Results will be presented as mean +/-SD for continuous normally distributed variables, as median (interquartile range) for continuously non-normally distributed data and as percentages for categorical data. Significant changes in clinical symptom improvement, arterial flow and biochemical variables over time will be assessed using ANOVA for repeated measurements. A P value < 0.05 will be considered statistically significant.
Study duration & dates	Total of 24-month recruitment period. From Q1 - 2018 to Q3 - 2019. Study duration is 6 months from the initial angiographic procedure

PATIENT FLOW DIAGRAM

STUDY SCHEDULE

Assessments and Recordings	V1	V2	Phone Call	V3	Phone Call	Phone Call	V4
	Screening and Baseline	Day 30 (+7 days)	Day 60	Day 90 (+21 days)	Day 120	Day 150	Day 180 (+ 21 days)
Subject Information	X						
Informed Consent	X						
Inclusion/Exclusion Criteria	X						
Demographics	X						
Medical History	X						
Confirmation of eligibility	X						
Laboratory tests							
FBC	X	X		X			
ESR	X	X		X			
EUC	X	X		X			
Liver Function Tests	X	X		X			
Lipid Studies	X	X		X			
CK-MB	X	X		X			
High Sensitivity Troponin T	X	X		X			
High Sensitivity CRP	X	X		X			
Pregnancy testing	X						
C. pneumoniae macrophage cultures	X			X			
C. pneumoniae titers	X			X			
C. pneumoniae DNA detection	X			X			
Physical Examination	X	X		X			
Vital Signs	X	X		X			
Quantitative Coronary Angiogram	X			X			
ECG	X			X			
New York Heart Association Functional Class	X	X		X			
Fractional Flow Reserve, Pressure/flow wire measurements and intracoronary imaging (IVUS + OCT)	X			X			
Concomitant medications	X	X	X	X	X	X	X
Concomitant illnesses	X	X	X	X	X	X	X

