In subjects with stable coronary heart disease (CHD) and inducible ischemia, percutaneous coronary interventions (PCI) can improve symptoms. As coronary angiography is often inexact in accurately determining the functional significance of non-critical coronary stenoses, fractional flow reserve (FFR) can assess their physiological significance¹². For subjects with acute coronary syndromes and multivessel disease undergoing an early invasive strategy, performing PCI in the culprit vessel and 'staging' possible treatment allows measurement of non culprit FFR at initial angiography. While non-culprit FFR in Acute Coronary Syndrome (ACS) subjects may worsen acutely due to endothelial dysfunction, randomisation should minimise confounding. Return for planned staged PCI as guided by angiography has been standard practice in such subjects, and increasingly, revascularisation is FFR guided. We plan to perform another FFR study to evaluate flow changes over a three month period.

The coronary circulation is comprised of two major components: the major epicardial coronary arteries which have a capacitance function; and the microvascular circulation comprised of pre-arterioles and arterioles which provide a metabolic interface with cardiac myocytes.¹³ Both components of the circulation have been implicated in coronary ischaemia. By measuring pressure and flow in the epicardial coronary artery, indices to assess the microcirculation can be calculated such as CFR, IMR, HSR, HMR at the same time as calculating the FFR value. This provides a comprehensive physiological assessment of the entire coronary circulation¹⁴. We plan to record pressure and flow indices at the time of measurement of FFR in the culprit and non-culprit arteries.

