7.2.2 Safety data

7.2.2.1 Laboratory Studies

A blood sample will be collected at each visit. The following blood tests will be performed: Full blood count, Full biochemistry as per detailed in 7.2.1.1. Additional tests may also be requested by the physician, but will not be part of the study unless related to adverse events.

The reference ranges for normal laboratory values and current certificate of NATA accreditation will be obtained from the relevant laboratories before the study commences.

Values outside the normal range will be noted in the CRF and those considered to be of clinical significance, particularly those related to the study medication, will be recorded as adverse events. Values outside the normal range will be monitored until they have been stabilised.

Comparison of pre and post treatment C. pneumoniae parameters will be assessed to show efficacy of the ACAC combination.

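### Section 11.1 and the synopsis name different methods for change over time in arterial flow, symptoms and biochemistry, and neither states a treatment-versus-control contrast

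*Combined protocol and SAP*

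**What the plan says.** The primary objective (section 2.1) is the effect of the combination on coronary flow as determined by FFR. Section 3 describes a 1:1 randomised, placebo-controlled trial. FFR is measured twice, at baseline and at Visit 3 (section 7.2.1.5).

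The analysis text is in three places:

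- **Section 11.1:** changes in "arterial flow, clinical symptoms and biochemical variables over time compared with that baseline will be assessed using an analysis of covariance".
- **Synopsis, Statistical procedures:** changes in clinical symptom improvement, "arterial flow and biochemical variables over time will be assessed using ANOVA for repeated measurements".
- **Section 7.2.2.1:** "Comparison of pre and post treatment C. pneumoniae parameters will be assessed to show efficacy of the ACAC combination".

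One sentence ties both arms to a named test. It follows the ANCOVA sentence in section 11.1: "Differences between treatment and control groups in the occurrence of FFR" at or above the threshold are tested by Fisher's exact test.

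Two other statements bear on the reading. Section 11.1 says that efficacy analyses will "include all subjects who received the combination antibiotic therapy", without mentioning placebo recipients. The Introduction says the second FFR study is done "to evaluate flow changes over a three month period". It also says that non-culprit FFR in acute coronary syndrome "subjects may worsen acutely due to endothelial dysfunction, randomisation should minimise confounding".

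**The concern.** Two analysts could follow this plan and report different tests. One would compare Day 90 FFR between arms, adjusted for baseline. The other would test whether FFR, symptoms or laboratory values changed from baseline, either in all subjects or within the active arm.

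The second analysis does not isolate the drug effect. Two sources of change act on both arms. Subjects enter because a measured FFR was ≤0.80 (section 4.1, criterion 4), so some of the low baseline values are measurement error that will not recur. The Introduction also says that non-culprit FFR may be acutely depressed in acute coronary syndrome, so some recovery by Day 90 is plausible without any drug effect. The Introduction relies on randomisation to deal with this, and randomisation protects only a contrast between arms.

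Section 11.3 says the study should generate hypotheses for later trials. For that purpose the most useful product on the primary objective is a between-arm FFR difference with a confidence interval. No sentence in the plan asks for one.

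**Working it through.** **1. The passages side by side.**

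| Place | Variables | Method | Arm named? |
|---|---|---|---|
| 11.1 | Arterial flow, clinical symptoms, biochemistry | ANCOVA, relative to baseline | No |
| Synopsis | Clinical symptom improvement, arterial flow, biochemistry | Repeated-measures ANOVA | No |
| 7.2.2.1 | C. pneumoniae parameters | Before versus after treatment | No |
| 11.1, next sentence | FFR at the threshold | Fisher's exact test | Yes |

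The authors named both arms where they specified a contrast. The sentence before it does not.

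**2. What a time-only test estimates.** Let both arms share a change c and let the drug add d. With equal arms the pooled mean change is (c + (c + d))/2 = c + d/2. If d = 0, the test still responds to c. The between-arm difference is (c + d) − c = d.

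**3. How large c can be from selection alone.** The documents give no FFR mean or SD, so these inputs are assumptions: lesion FFR mean 0.77 and SD 0.06 before selection; measurement SD m of 0.02 or 0.03; SD of true change 0.03 or 0.05; 60 pairs, 30 per arm. The cut at 0.80 and the 60 pairs are the protocol's.

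Formulas: s = √(0.06² + m²); a = (0.80 − 0.77)/s; λ = φ(a)/Φ(a). The selected mean lies sλ below 0.77. The fraction u = m²/s² of that gap is measurement error and returns at the next measurement.

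- m = 0.02: s = 0.0632, a = 0.474, λ = 0.3565/0.6824 = 0.522. Gap 0.0330, u = 0.10, expected rise 0.0033.
- m = 0.03: s = 0.0671, a = 0.447, λ = 0.3610/0.6726 = 0.537. Gap 0.0360, u = 0.20, expected rise 0.0072.

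Selection alone therefore raises mean measured FFR by about 0.003–0.007 in an untreated arm.

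**4. False-positive rate of a pooled change-over-time test, no drug effect.** The variance of measured change is (change SD)² + m² + v, where v is the baseline error variance after selection: v = m²(1 − u) + u²s²(1 − aλ − λ²).

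- Lowest case (m = 0.02, change SD 0.05): SD = √(0.0025 + 0.0004 + 0.00038) = 0.0573. SE = 0.0573/√60 = 0.0074. Shift = 0.0033/0.0074 = 0.45. Two-sided rejection probability at 5% is about 7%.
- Highest case (m = 0.03, change SD 0.03): SD = √(0.0009 + 0.0009 + 0.00081) = 0.0510. SE = 0.0066. Shift = 0.0072/0.0066 = 1.09. Rejection probability is about 19%.

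Simulation over all four noise settings (10,000 runs each) gives 7–19%. An assumed common rise of 0.01 in both arms takes this to 42–74%. Between-arm ANCOVA stays at 4.5–5.5%.

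**5. Does ANCOVA versus ANOVA matter for FFR?** With two time points, a group-by-time term in the synopsis ANOVA is a between-arm comparison of change scores. Under the same assumptions, the ratio of its variance to that of ANCOVA is 0.98–1.02. For FFR the missing arm term is the defect. The choice between the two methods is secondary.

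**The case against.** The strongest reply is that ANCOVA in a randomised two-arm trial implies a treatment factor. FFR has only two measurements. If baseline is the covariate, Day 90 is the only outcome left and arm is the obvious factor to test. Section 11.1 also opens by invoking intention to treat. This largely stands: a between-arm ANCOVA is the most natural reading of section 11.1, and the 7–19% does not describe it. That figure applies only to a literal reading of the synopsis and rests on assumed standard deviations. The higher rates also need an assumed common rise that no passage gives.

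The reply does not remove the conflict. The synopsis names another method, and section 7.2.2.1 explicitly offers a before-after comparison as evidence of efficacy.

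A reader might infer stronger things that the documents do not support:

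- *That the primary efficacy result is uncontrolled.* Section 3 defines the primary endpoint against the control group, and section 11.1 gives it a between-arm Fisher test.
- *That the efficacy-set wording drops placebo subjects.* The Fisher sentence in the same paragraph includes a control group.
- *That FFR itself is to be judged before versus after.* Section 7.2.2.1 concerns C. pneumoniae parameters only.
- *That New York Heart Association class falls under these two sentences.* Neither mentions it, and section 7.2.1.3 lists it separately from symptoms.

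**Conclusion.** The point holds as an inconsistency and an omission: two methods for essentially the same variables, no stated arm contrast in either place, and one explicit before-after efficacy comparison. It should be corrected before unblinding, because choosing the model afterwards would be open to data-driven selection. It does not undermine the primary comparison at 0.80.

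That the contrast is missing rests on the text alone. The size is illustrative. Under the assumptions above, the literal synopsis test has a false-positive rate of 7–19% with no common rise, against about 5% for between-arm ANCOVA. The documents do not supply the inputs needed to narrow that range. No error rate was calculated for the C. pneumoniae comparison; the objection to it is that change shared by both arms would count as drug effect.

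**What to change.** 1. **Section 11.1, FFR.** State that Day 90 FFR is compared between arms by ANCOVA, with arm as factor and baseline FFR as covariate, in subjects with paired FFR. Report the adjusted difference (ACAC minus placebo) with its 95% CI as a supporting analysis of the primary objective. Under the assumptions above, the expected half-width is 0.021–0.033.
2. **Section 11.1, other outcomes.** State the same baseline-adjusted arm contrast for the biochemical variables, on the log scale where section 11.1 already calls for it, and for other outcomes with one value per subject. State an arm contrast for symptoms too, in a form that suits the severity scale used. Where a measure is taken in both culprit and non-culprit arteries (pressure/flow indices, sub-study imaging), analyse each vessel type separately or allow for within-subject correlation. Section 11.1 says of subjects without paired FFR that "All other subjects will be included in secondary analyses", so name the analysis set for each outcome.
3. **Section 7.2.2.1.** Compare Day 90 C. pneumoniae results between arms instead of before versus after treatment.
4. **Synopsis.** Align it with section 11.1, and label within-arm changes as descriptive.

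The cost is wording in three places. No new data, visits or subjects are needed, and the primary endpoint and its Fisher test stay unchanged.

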12. ETHICAL AND LEGAL ASPECTS

12.1 Good Clinical Practice

The procedure set out in this study protocol, pertaining to the conduct, evaluation, and documentation of this study, are designed to ensure that the Sponsor and Investigator abide by the principles of the NIH Good Clinical Practice (GCP) guidelines of the Therapeutic Goods Administration (TGA) published in CPMP/ICH/135/95 July 2000 and the ethical principles laid down in the current revision of the Declaration of Helsinki 2004 (Appendix 5) and the NHMRC National Statement on Ethical Conduct in Human Research 2007. The study will also be carried out in keeping with local legal and regulatory requirements.

12.2 Delegation of Investigator Responsibilities

The investigator should ensure that all persons assisting with the trial are adequately informed about the protocol, the study treatments, and their trial-related duties and functions.

The investigator should maintain a list of co-investigators and other appropriately qualified persons to whom he or she has delegated significant trial-related duties.

12.3 Subject Information and Informed Consent

Before being admitted to the clinical study, the subject must consent to participate after the nature, scope, and possible consequences of the trial have been explained in a form understandable to him or her.

An informed consent document that includes both information about the study and the consent form will be prepared and given to the subject. The document must be in a language understandable to the subject and must specify who informed the subject. The person who informs the subject must be a physician.

After reading the informed consent document, the subject must give consent in writing. The subject's consent must be confirmed at the time of consent by the personally dated signatures of; the subject, person conducting the informed consent discussions, and a witness.

It is recommended that the investigator inform the subjects' primary physician (GP) about the subjects' participation in the trial if the subject has a primary physician and if the subject agrees to the primary physician being informed.

12.4 Confidentiality

Only the Subject Number and Subject initials will be recorded in the Case Report Form, and if the Subject name appears on any other document (e.g. pathologist report), it must be obliterated before a copy of the document is supplied with the CRF. Study findings stored on a computer will be stored in accordance with local data protection laws. The subjects will be told that representatives of the Sponsor, HREC, or regulatory authorities may inspect their medical records to verify the information collected, and that all personal information made available for inspection will be handled in strictest confidence and in accordance with local data protection laws.

The Investigator will maintain a confidential Subject identification list (Subject numbers with the corresponding Subject names) to enable records to be identified.

12.5 Protocol Amendments

Neither the investigator nor the sponsor will alter this study protocol without obtaining the written agreement of the other. Once the study has started, amendments should be made only in exceptional cases. The changes then become part of the study protocol.

12.6 Approval of the Study Protocol and Amendments

Before the start of the study, the study protocol, informed consent document, and any other appropriate documents will be submitted to the institutional ethics committee (HREC) with a cover letter or a form listing the documents submitted, their dates of issue, and the site for which approval is sought. If applicable the documents will also be submitted to the authorities, in accordance with local legal requirements (CTN).

Study medication can only be accessible to the investigator for study use after documentation on **all** ethical and legal requirements for starting the study has been received by the sponsor. This documentation must also include a list of the members of the HREC and their occupations and qualifications. If the HREC will not disclose the names of the committee members to the Sponsor, it should be asked to issue a statement confirming that the composition of the committee is in accordance with GCP and NHMRC guidelines. Formal approval by the HREC should preferably mention the study title, study code, study site, and any other documents reviewed. It must mention the date on which the decision was made and must be officially signed by a committee member.

Before the first subject is enrolled in the study, all ethical and legal requirements must be met. The HREC and, if applicable, the authorities must be informed of all subsequent amendments, in accordance with local legal requirements. Amendments must be evaluated to determine whether formal approval must be sought and whether the informed consent document should also be revised. If formal HREC approval is required then the amendments must not be implemented until approval is granted.

The investigator must keep a record of all communication with the HREC and, if applicable between a coordinating investigator and the HREC. This also applies to any communication between the investigator (or coordinating investigator, if applicable) and the authorities.

12.7 Ongoing Information for HREC

If required by legislation or the HREC, the investigator must submit to the HREC:

- Information on serious or unexpected adverse events as soon as possible.
- Periodic reports on the progress of the study.

12.8 Premature Closure of the Study

The sponsor or the investigator has the right to close this study at any time. As far as possible, this should occur after mutual consultation. The HREC must be informed, if required by legislation.

Should the study be closed prematurely, all study materials (completed, partially completed, and blank case report forms, study medication, etc) must be returned to the sponsor, as if the study had been completed.

12.9 Record Retention

The following records must be retained by the investigator for a *minimum* of 15 years after the completion or termination of the study:

- Signed informed consent documents for all subjects
- Subject identification code list, screening log (if applicable), and enrolment log
- Record of all communications between the investigator and the HREC
- Composition of the HREC (or other applicable statement as described in section 12.6 Approval of the study protocol and amendments)

- Record of all communications between the investigator and sponsor
- List of sub investigators and other appropriately qualified persons to whom the investigator had delegated significant trial-related duties, together with their roles in the study and their signatures
- Copies of case record forms and of documentation of corrections for all subjects
- Drug accountability records
- Records of any body fluids or tissue samples obtained
- All other source documents (subject records, hospital records, laboratory records etc)

Normally, these records will be held in the investigator's archives. If the investigator is unable to meet this obligation, he or she must ask the sponsor for permission to make alternative arrangements. Details of these arrangements should be documented.

